82 symptoms of PTSD and depression when re-assessed at one year post-deployment [25], and sleep
83 problems are better predictors of suicide among military personnel than measures of either depression or
84 hopelessness [26]. Thus, sleep may be a leverage point for affecting recovery from PTSD.

85 Research on conditioned fear points to a critical role for sleep in the treatment of PTSD. Indeed,
86 PTSD has been conceptualized as a disorder of fear conditioning, involving hyper-responsive fear
87 reactions via sustained and exaggerated amygdala activation [27]. There is a large animal literature
88 showing that quality sleep facilitates the extinction of conditioned fear [28-31]. Moreover, Pace-Schott
89 and colleagues, recently demonstrated the same effect in humans [32], showing that after a person has
90 been conditioned to fear a particular stimulus and then provided with multiple extinction trials, the
91 extinction response only generalizes to other similar stimuli following a night of undisturbed sleep, but
92 fails to generalize to other similar stimuli if post-learning sleep is prevented. These results suggest that
93 extinction of conditioned fear is facilitated by sleep. Other research shows that sleep disruption amplifies
94 the effects of anxiety on anticipatory brain functioning in the amygdala [33]. By extension, the potential
95 for rapid recovery from PTSD may be hampered by the inability to obtain normal restorative sleep. In
96 other words, the PTSD patient may be locked in a vicious circle whereby one of the major symptoms of
97 the disorder may itself be preventing full recovery and leading to continuation or even exacerbation of
98 symptoms. Therefore, effective treatment and recovery from PTSD may be crucially dependent upon, or

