**FORM: Application for Human Research**

| NUMBER | FORM DATE | PAGE |
|--------|-----------|----------|
| F200 | 02/2014 | 14 of 44 |

360 function, alterations in proton metabolites in the limbic system and medial prefrontal cortex, and reduced
361 PTSD symptom severity at follow-up assessment. The following are the Specific Aims and Hypotheses:

362 **AIM 1:** Evidence suggests that morning bright light therapy suppresses daytime melatonin and
363 leads to an entrainment of the circadian rhythm that modulates daytime alertness and nighttime sleep.
364 The first objective will be to assess the validity of this effect in PTSD patients.

365 **Hypothesis 1: Six weeks of BLT will improve sleep relative to PL among PTSD subjects.**

366 **1a:** Six weeks of morning blue light therapy (BLT) will improve objective and subjective
367 measures of sleep duration and quality as measured by actigraphy, sleep logs, sleep scales, and
368 polysomnography relative to an amber light placebo therapy (PL) condition.

369 **AIM 2:** If light therapy is successful in entraining the circadian rhythm and improving nighttime
370 sleep in patients with PTSD, this should be associated with improvement in symptoms and cognitive
371 functioning, as sleep has been shown to be critical in the process of extinguishing conditioned fears.
372 Therefore, the second Aim is to evaluate the association between changes in sleep patterns and
373 improvement in symptom expression, emotional wellbeing, and cognitive functioning in patients with
374 PTSD. However, even if Aim 1 is not successful, the present study will provide important cross-sectional
375 data regarding the relationship between measured sleep, cognitive functioning, and fear extinction in
376 individuals with PTSD.

377 **Hypothesis 2: BL will improve cognitive functioning, symptoms of PTSD, and generalization of**
378 **fear extinction relative to PL.**

379 **2a:** Six weeks of BL will improve measures of neurocognitive (i.e., memory and executive
380 functions) and mood functioning relative to PL.

381 **2b:** The PTSD group receiving six weeks of BL will show significant reduction in self-
382 reported symptom scores on the PTSD symptom checklist and CAPS, lower emotional distress on clinical
383 measures, and greater *generalization of conditioned fear extinction* relative to the PTSD group receiving
384 PL.

385 **AIM 3:** At present, there are no known studies that have examined the neurobiological correlates

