386 of symptom improvement in patients with PTSD following light exposure therapy. The present study
387 aims to provide clear evidence of functional and neurochemical changes that are associated with changes
388 in sleep, cognition, and PTSD symptoms from pre- to post-treatment. Even if Aim 1 is not supported, the
389 obtained cross sectional data will provide critical insights regarding the association between sleep,
390 neurometabolites, and brain function within patients with PTSD. This correlational information is
391 currently lacking for PTSD and will fill an important knowledge gap regardless of whether the light
392 therapy is successful.

393 **Hypothesis 3: Six weeks of BL will produce reliable changes in brain activation and**
394 **neurochemistry relative to PL, particularly for PTSD subjects.**

395 **3a:** Relative to PL, six weeks of BL will lead to significantly increased ventromedial
396 prefrontal activation and reduced amygdala activation during the backward masked affect fMRI task.

397 **3b:** Relative to PL, six weeks of BL will lead to significantly greater negative functional
398 connectivity between the ventromedial prefrontal cortex and amygdala during resting state fMRI.

399 **3c:** Relative to PL, six weeks of BL will be associated with increased activation of the
400 VMPFC, and reduced activation within the amygdala and dorso-medial prefrontal cortex during the
401 extinction recall scan.

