 837 the US. During the Extinction phase, one CS+ color (CS+E) appears 16 times in the extinction context,
 838 along with 16 interspersed CS-s and no USs. The other CS+ color (CS+U) does not appear and therefore
 839 remains un-extinguished. During the Extinction Recall phase, the 8 CS+Es and 8 CS+Us are presented in
 840 the extinction context with 16 interspersed CS-s and no USs. The measurement of conditioned fear is

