**FORM: Application for Human Research**

| NUMBER | FORM DATE | PAGE |
|--------|-----------|----------|
| F200 | 02/2014 | 26 of 44 |

841 palm-recorded skin conductance response (SCR), a reliable index of sympathetic activation. Participants
842 will be conditioned and undergo extinction prior to entry into the scanner. During scanning, participants
843 will again be confronted with the previously extinguished stimuli to evaluate extinction recall, a hallmark
844 deficit of PTSD. It is expected that improved sleep due to the BL condition will lead to improved
845 generalization of the extinction response and extinction recall.

846 **Modified Sleep Latency Test (MSLT):** Participants will undergo 3 MSLT procedures with
847 polysomnographic (PSG) recording over the course of the assessment day. A trained technician will fit
848 each participant with a standard electrode montage for PSG recording. Standard PSG will be recorded
849 using the Polysmith 11.0 system that is installed in our sleep laboratory facilities. During each MSLT, the
850 participant will be given up to 20 minutes to fall asleep in a private, darkened, sound-attenuated bedroom.
851 PSG recordings will be scored by a trained technician to determine the latency to fall sleep. The mean
852 latency to sleep is taken as an indication of objective sleepiness.

853 **Psychomotor Vigilance Test (PVT):** The PVT is a 10-minute computerized measure of
854 sustained attention and psychomotor vigilance that has been shown to be exquisitely sensitive to sleep
855 deprivation. The PVT currently serves as the “gold standard” for assessing degradation in alertness and
856 vigilance following sleep loss.

857 **Functional Neuroimaging:** Subjects will be screened for any contraindications to MRI and magnetic
858 materials. The investigator or MRI Technologist will explain the MRI system and the scan that they are
859 about to take part in. The subject will be asked to lie down on the scanner bed. Some part of the subject's
860 body may be covered or enclosed within an FDA or UA HSPP approved MRI coil. The subject may be
861 asked to interact with a peripheral system such as a button, joystick, or TV system before, during, or after
862 the scan.

863 Blood Oxygen Level Dependent (BOLD) functional magnetic resonance imaging (fMRI) will
864 be collected at the University of Arizona Translational Bioimaging Resource. The MRI hardware and

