 887 amygdala response has been found on this task in patients with PTSD [27]. Our laboratory has extensive
 888 experience using this task with patients with PTSD and anxiety disorders [27, 111-115], and healthy
 889 adults and children [116-118].

890 2. Extinction Recall (ER): This task measures the
 891 retention of the extinction memory established during the
 892 previous fear conditioning session. While undergoing fMRI,
 893 participants will view the previously conditioned images from
 894 the Fear Conditioning and Extinction Task. Here, 8 CS+E, 8
 895 CS+U, and 16 CS- trials will be presented (without any
 896 shocks). Skin conductance responses will also be collected
 897 while participants are undergoing the scan. During this task,
 898 the contrast of interest will be CS+E vs. CS+U, permitting the
 899 isolation of psychophysiological and brain responses that are
 900 specific to extinction recall.

901 3. Resting State Scan (RS): Emerging evidence suggests
 902 that the brain shows stable patterns of functional connectivity
 903 during the resting state and that these patterns may be
 904 particularly useful in elucidating specific networks [119-122].
 905 Therefore, in addition to the probe tasks described above subjects will also be scanned for 10 minutes
 906 with eyes closed and instructed to let their "mind wander." Functional connectivity will be evaluated
 907 from pre- to post-treatment for the two conditions.

908 4. Anticipation Task: The Emotional Anticipation Task was adapted on the basis of Aupperle et al.'s
 909 (2013) study design and lasts a total of 7 min and 8 seconds. Two version of the anticipation tasks will be
 910 used, in order to have two different versions of the tasks for the baseline and follow up visit. Participants
 911 are presented with a grey background with a black arrow alternating randomly in its direction from left to
 912 right (Baseline). Participants are instructed to indicate via button press which direction the arrow was
 913 pointing in. Participants are told that when the screen turns yellow, a negative picture will soon appear
 914 (Negative Anticipation (NA)). If the screen turns blue, a positive picture will soon appear (Positive
 915 Anticipation (PA)), and if the screen turns green a positive *or* a negative picture will soon appear
 916 (Uncertain Anticipation (UA)). The picture stimuli consist of positive and negative pictures from the

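### The one contrast named for extinction recall, CS+E vs. CS+U, sets the predicted recall and generalization effects against each other, and generalization has no measure of its own

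*Combined protocol and SAP*

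**What the plan says.** All of this is in the combined protocol and SAP.

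- **Fear Conditioning Paradigm (section 7, Procedures).** Two vehicle colours are paired with shock and a third, CS-, never is. Only one shocked colour, CS+E, is shown during extinction. "The other CS+ color (CS+U) does not appear and therefore" is left unextinguished. Conditioned fear is measured by skin conductance response (SCR). Improved sleep under BL is expected to give better "generalization of the extinction response and extinction recall".
- **Hypothesis 2b (Specific Aims).** Besides lower PTSD checklist and CAPS scores and less distress, it predicts greater "generalization of conditioned fear extinction" under BL than PL.
- **Background, sleep disruption in PTSD.** This is where the term is given a meaning: the "extinction response only generalizes to other similar stimuli following a night of undisturbed sleep, but" not when sleep after learning is prevented.
- **Functional Neuroimaging, task 2, Extinction Recall.** The scan shows 8 CS+E, 8 "CS+U, and 16 CS- trials will be presented (without any" shocks). Then "the contrast of interest will be CS+E vs. CS+U, permitting the" "isolation of psychophysiological and brain responses that are" specific to recall of extinction.
- **Hypothesis 3c.** It expects increased activation of the "VMPFC, and reduced activation within the amygdala and dorso-medial prefrontal cortex during the" recall scan. It names no contrast.
- **Data Analysis (section D).** No generalization measure and no contrast against CS- is defined. The region-of-interest paragraph lists regions for the masked affect and interference tasks, but not for extinction recall.

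**The concern.** CS+U was conditioned, resembles CS+E and never went through extinction. On the Background's account, extinction that generalizes should lower the response to it. The protocol expects BL to produce that effect together with better recall. The only stated contrast then subtracts one from the other.

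Two things are at stake. The recall comparison loses signal whenever generalization occurs, so a weak or null result could be read as failure of recall when both effects are present. And the generalization that Hypothesis 2b predicts cannot be shown by this contrast, in which it counts against the treatment; no other measure is offered.

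**Working it through.** **1. The plan's own power figure.** The Power Analysis states 0.99 for the treatment-by-session interaction, with N = 90, f = 0.25 and alpha = 0.05. The noncentrality is lambda = f² × N × m / (1 - rho), with m = 2 sessions and df 1 and 88. The pre-post correlation rho is not stated.

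- rho = 0.5: 0.0625 × 90 × 2 / 0.5 = 22.5, power 0.997
- rho = 0.3: 16.07, power 0.978
- rho = 0: 11.25, power 0.913

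The stated 0.99 lies between the first two, so it is attainable at a moderate rho. At rho = 0.5 it corresponds to a difference in change scores of sqrt(22.5 / (45/2)) = 1.0 SD. It refers to a single outcome with no subtraction between cues.

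**2. The sign argument (no figures needed).** Relative to PL, let BL lower the change in response by a for CS+E and by g for CS+U, and leave CS- unchanged.

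- CS+E minus CS+U: -a + g = -(a - g)
- CS+E minus CS-: -a
- CS+U minus CS-: -g

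The named contrast gives the full recall effect only if g = 0. It is halved at g = a/2 and zero at g = a. For VMPFC, where activation is expected to rise, the signs flip but the subtraction is the same.

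**3. Illustration of size.** The documents give no expected CS+E or CS+U effects, so these inputs are assumptions: a = 1.0 SD (the effect implied in step 1) or 0.5 SD; the change in response to each cue has the same SD; the correlation r between changes for two cues is 0.5. The standardized effect is d = (a - g) / sqrt(2(1 - r)). The test is a two-sided two-sample t test with 45 per arm, df 88 and noncentrality d × sqrt(45/2). Example: a = 1.0, g = 0.5 and r = 0.5 give d = 0.5 / 1 = 0.5, noncentrality 2.37 and power 0.65.

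| g as a share of a | CS+E vs. CS+U, a = 1.0 | CS+E vs. CS+U, a = 0.5 | CS+U minus CS-, a = 1.0 | CS+U minus CS-, a = 0.5 |
|---|---|---|---|---|
| 0 | 0.997 | 0.65 | – | – |
| 0.25 | 0.94 | 0.42 | 0.22 | 0.09 |
| 0.5 | 0.65 | 0.22 | 0.65 | 0.22 |
| 0.75 | 0.22 | 0.09 | 0.94 | 0.42 |
| 1 | 0.05 | 0.05 | 0.997 | 0.65 |

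CS+E minus CS- keeps power 0.997 (a = 1.0) or 0.65 (a = 0.5) in every row. The result depends on r: at half generalization and a = 1.0, the named contrast has power 0.38, 0.65 and 0.86 for r = 0, 0.5 and 0.7; at a = 0.5 it has 0.13, 0.22 and 0.33.

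**4. What the CS- contrasts would let in.** Conditioning is repeated at Visit 3, after treatment. Suppose BL also weakens acquisition, lowering the response to both conditioned cues by c. Then CS+E minus CS- moves by -(a + c) and CS+U minus CS- by -(g + c), while CS+E minus CS+U still moves by -(a - g), because c drops out. The CS- contrasts separate a from g only if c is small or accounted for.

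**The case against.** The strongest reply is that the contrast does its stated job. The protocol assigns it to recall, not to Hypothesis 2b, and a conditioned but unextinguished cue is a deliberate control for general change in fear reactivity. Step 4 supports this: CS- contrasts alone could score weaker conditioning as generalization. That stands, and it is a reason to keep CS+E vs. CS+U. It does not supply a generalization measure, and it does not protect the recall contrast from an effect that the protocol itself predicts on CS+U.

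A second reply is that the protocol never calls CS+U the generalization probe. The Background refers to a night of sleep, whereas here conditioning and extinction precede the scan within the assessment visit, with no intervening night described. So the documents do not show that g would be large. That also stands. But CS+U is the only similar unextinguished cue in the task; if another probe is intended, it is not named.

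A reader might infer that an effective treatment is likely to produce a null or reversed result, or that the contrast shrinks as the treatment works better. The documents do not support this. The contrast grows with a and shrinks only if g rises faster than a. Cancellation needs equal effects. Reversal needs a larger gain on the cue that was never extinguished, which nothing in the documents suggests.

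**Conclusion.** The point holds in limited form. The named contrast cannot separate the two effects predicted for BL: they enter with opposite signs, any generalization attenuates the recall contrast, and equal effects would cancel. This rests on reading generalization as carry-over to CS+U. On any reading, the generalization component of Hypothesis 2b lacks a stated measure.

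It would go too far to say that Hypothesis 2b as a whole cannot be confirmed, since its checklist, CAPS and distress components are untouched. Hypothesis 3c is affected only if the Extinction Recall contrast is the one used for it; the protocol states no other for that scan. The power figures show how attenuation behaves under assumed effects and correlations. They do not estimate the loss in this trial, and the stated 0.99 is not itself shown to be wrong.

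**What to change.** Keep CS+E vs. CS+U as the specificity contrast. Pre-specify alongside it, for both SCR and fMRI:

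- CS+E minus CS- for extinction recall
- CS+U minus CS- for generalization (Hypothesis 2b)

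State the expected direction of each contrast, by region for fMRI, and say which one tests Hypothesis 3c. Take the acquisition-phase CS+ minus CS- response at each visit into account, so that weaker conditioning is not scored as generalization. Acquisition at Visit 3 is itself measured after treatment, so compare it between arms and report that result beside the adjusted analysis.

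No new data are needed: the 16 CS- trials are already presented. The cost is analysis wording and a larger multiplicity adjustment. Two contrasts are added per outcome; with SCR and the three regions in Hypothesis 3c, that is up to 2 × 4 = 8 further comparisons if all are tested.
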